5.0 STUDY POPULATION

Prospective approval of protocol deviations to recruitment and enrollment criteria, also known as protocol waivers or exemptions, is not permitted.

5.1 Inclusion Criteria

Subjects are eligible to be included in the study only if all of the following criteria apply:

1. Male and female subjects 2 to 17 years of age, inclusive.
2. Confirmed diagnosis of atopic dermatitis according to the Hanifin and Rajka criteria.
3. A minimum of 10% but no more than 60% of the subjects' body surface area (see [Appendix 6](#) for guidance) is affected by atopic dermatitis (affected is defined by physical examination findings: erythema, edema, scaling, lichenification, and excoriation; with the excoriation serving as the physical examination correlate of pruritus).
4. A vIGA-AD scale of 2 or 3 at Screening and Baseline.
5. Subject, or the parent or guardian, to provide written informed consent and authorization for protected health information disclosure.
6. Subjects must be generally in good health based on Investigator's assessment (other than atopic dermatitis).
7. Normal vital signs, or with no clinically significant vital signs that in the opinion of the Investigator, would place the subject at increased risk or would confound the objectives of the study.
8. Females must not be pregnant, as confirmed by negative urine pregnancy testing. Female subjects aged ≥ 11 years old, or female patients < 11 years old who have started menstruating, will have urinary pregnancy test performed at Screening and prior to the first dose with negative results in order to participate in the study. Females must either practice abstinence from heterosexual contact or use one of the highly effective contraceptive options described in the [Appendix 5](#).
9. Male subjects of reproductive potential, must be willing to practice effective contraception during the study while receiving study treatment from Day 1 and for 7 days after the last study visit (Day 28).
10. Ability to comprehend and comply with study procedures.
11. Agree to commit to participate in the current protocol.
12. Provide written informed consent prior to any study procedure being performed.

5.2 Exclusion Criteria

Subjects are excluded from the study if any of the following criteria apply:

1. Clinically significant physical or mental disorder which, in the opinion of the Investigator, would place the subject at increased risk or would confound the objectives of the study.
2. Subjects with atopic dermatitis on the face only.

3. Active cutaneous bacterial, viral or fungal infection in any treatment area at Baseline (eg, clinically infected atopic dermatitis).
4. History or presence of immunological deficiencies or diseases, organ transplant, human immunodeficiency virus (HIV), diabetes, malignancy, malignant or pre-malignant skin conditions, serious active or recurrent infection, systemic immunosuppressive regimens, clinically significant renal disease severe hepatic disorders, or other severe uncontrolled conditions (eg, drug or alcohol abuse), that are significant and/or that may pose a health risk to the subject in the study or may have an impact on the study assessments.
5. Unstable atopic dermatitis or a consistent requirement for high-potency corticosteroids (class I-III steroids).
6. Active systemic or localized infection (including infected AD).
7. Subjects unable to comply with the excluded medication/therapy restriction listed in [Appendix 4](#).
8. Known hypersensitivity to the study treatment.
9. Known to have hepatitis B, hepatitis C or HIV I or II tests. Details will be recorded in medical history, a blood sample will not be collected for confirmation.
10. Female subject who is pregnant, breastfeeding, or considering pregnancy during the study.
11. Any skin condition which in the Investigator's opinion may interfere with the evaluation of atopic dermatitis.
12. Use of any investigational drugs within the previous 30 days prior to dosing or within a period of less than 5 times the drug's half-life, whichever is longer.
13. Use of any biologic within a period of 5 times its half-life.
14. Children or relatives of the Sponsor, clinical research organization, or the Study Site personnel are excluded from participating in the study.

5.3 Lifestyle Considerations

There are no dietary or activity related restrictions for this study.

5.3.1 Use of Cleanser and Moisturizer During the Study

At the beginning of the study, subjects will be provided with cleanser and moisturizer to use for the duration of the study as needed.

Subject should be advised to apply moisturizer 10 minutes after the application of the B244.

Subjects may not use other cleansers to wash their body for the duration of the trial. Subjects may use their preferred shampoo for the duration of the trial.

During Day 28 visit (End of B244 application) subjects will be asked to return cleanser and moisturizer that was provided to them by the Sponsor and will be asked to go back to their regular regimen and use their preferred cleanser and moisturizer.

Subjects will be encouraged not to use sunscreen during participation in the study. Sunscreen should be used minimally or used sparingly while in the active phase (Baseline to Day 28) of the study.

Subjects who do not have atopic dermatitis on their face may apply makeup as needed. However, those subjects who have atopic dermatitis on their face and require to use makeup will be advised to use it minimally.

5.4 Screen Failures

Screen failures are defined as subjects who consent/assent to participate in the clinical study but are not subsequently assigned to study treatment. A minimal set of screen failure information is required to ensure transparent reporting of screen failure subjects to meet the Consolidated Standards of Reporting Trials (CONSORT) publishing requirements and to respond to queries from regulatory authorities. Minimal information includes demography, screen failure details, eligibility criteria, and any SAE.

Individuals who do not meet the criteria for participation in this study (screen failure) may be rescreened on 1 occasion. Rescreened subjects should not be assigned the same subject number as for the initial screening.

6.0 INVESTIGATIONAL PRODUCT TREATMENT AND APPLICATION

Study treatment is defined as any investigational treatment(s), marketed product(s), placebo, or medical device(s) intended to be administered to a subject according to the study protocol.

6.1 Study Treatment(s) Administered

6.1.1 Investigational Product

Under normal conditions of handling and administration, the Investigational Product (IP) is not expected to pose significant safety risks to site staff. A Material Safety Data Sheet describing the occupational hazards and recommended handling precautions will be provided to site staff if required by local laws or will otherwise be available from the Sponsor upon request.

The IP must be stored in a secure area under the appropriate physical conditions for the product. Access to and administration of the IP will be limited to the Investigator and authorized site staff. The IP must be dispensed or administered only to participants enrolled in the study and in accordance with the protocol.

The Investigator is responsible for IP accountability, reconciliation, and record maintenance. The Investigator or designated site personnel must maintain IP accountability records throughout the course of the study. The responsible person(s) will document the amount of IP received from and returned to the Sponsor and the amount administered to subjects. The required accountability unit for this study will be the bottle. Discrepancies are to be reconciled or resolved.

Product name:	B244, 30 mL/bottle
Dosage form:	B244 suspension
Unit dose strength:	4x10 ⁹ cfu/mL
Route/administration/duration:	Topical application twice daily for 4 weeks
Physical description:	Odorless, cloudy, light pink suspension
Manufacturer/source of procurement:	AOBiome Therapeutics

Up to 6 bottles total will be dispensed to the subjects and will depend upon the body surface area affected by atopic dermatitis ([Appendix 6](#)) and the age of the subject ([Table 6.1](#)).

Table 6.1 Suggested Number of Bottles of B244 Issued to the Subject and Parent or Guardian

BSA (%)	2 to 5 years old	6 to 11 years old	12 to 17 years old
10	1 bottle	1 bottle	2 bottles
20	1 bottle	2 bottles	3 bottles
30	2 bottles	2 bottles	4 bottles
50	2 bottles	3 bottles	5 bottles

Table 6.2 Body Surface Area and Suggested Application of Investigational Product

Affected Body Surface Area	Approximate Number of Pumps per application		
	2 to 5 years old	6 to 11 years old	12 to 17 years old
10%	2	2	3
20%	3	4	7
30%	4	6	10
50%	7	10	16

At Baseline visit (Day1), all subjects will be dispensed up to 2 bottles of IP, depending on the number of lesions. Upon examining the subject, study staff will instruct the patient on the number of pumps to be applied per application for the duration of the treatment. If during the study participation subject develops new lesions, those should be treated as well.

It is suggested that subjects will use up to the number of bottles indicated in [Table 6.1](#) during participation in the trial, however this number should not exceed 6 bottles per subject per study. Study staff should monitor usage at every study visit and determine whether more IP should be dispensed to the subject based on age and usage, where the total number of pumps per application should not exceed 16.

Subjects and their guardians should use the details in [Table 6.2](#) to guide the suggested number of pumps to be applied on each application. Subjects will apply 1 pump (0.14 mL) of B244 (OD₆₀₀ 2.0 ± 0.4 equivalent to 4×10^9 cells/mL) per 200 cm² (approximately one adult palm size) of the affected area, twice a day approximately 12 hours apart, for 28 days (Day 1 to 28).

One pump should cover the surface area of skin the approximate size of one adult sized palm. One pump will be applied directly to the skin for each atopic dermatitis area that is the size of a palm of 1 adult sized hand.

The total number of bottles to be dispensed to the subjects will depend upon the body surface area affected by atopic dermatitis ([Appendix 6](#)), age of the subject and the number of areas affected by the disease.

The subject and parent or guardian of each subject will be instructed by clinical staff regarding the use of the spray pump and application of the dose to the area of atopic dermatitis. The first dose will be applied by the subject, parent or guardian in the study center under the supervision of the clinical staff.

For each dosing period, the subject under the supervision of the parent or guardian, or the parent or guardian, will dispense the required amount of study treatment using the pump. Whether the subject is likely to be able to apply the study treatment will be decided by the Investigator, or delegate, during the training session. If the subject is considered to be too young, or would be unreliable, to apply the study treatment the application will be done by the parent or guardian. Whenever the study treatment is applied by the subject the application must be under the supervision of the parent or guardian.

- The person applying the study treatment should wash his/her hands before and after applying study treatment.
- Subject should shake the bottle before each application and then saturate the application area well, holding the bottle approximately 6 inches away from the skin.
- Subjects will be asked to let the product air dry.
- Subjects may not wash for 2 hours post morning application of the IP.
- It is recommended that subjects may not bathe, shower or wash until the morning after the evening application of B244. For younger subjects who need cleaning related to diaper changes this is acceptable.
- While in use, one spray bottle may be stored at ambient temperature.
- DO NOT FREEZE
- The Sponsor will provide a biome friendly, preservative-free moisturizer and cleanser to be used as needed, at the discretion of the parent or guardian to clean the area of application before application of the treatment.
- The subject or parent or guardian will apply the study treatment to the affected area twice daily (approximately 12 hours apart) for 28 consecutive days.
- The parent or guardian will verify if the study treatment was applied as directed. Application details will be recorded in the study diary provided.
- Subjects will be asked not to expose the treatment kit to conditions which are unnatural or harmful to the product, such as excessive heat (temperatures over 77°F [25°C] and freezing temperatures [at 0°C]). Subjects may travel with their study medication but should not leave it in the hot car, outside in the cold temperatures etc. Subjects will also be asked not to tamper or cause damage to IP bottle.

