4.3 Justification for Dose

There are 3 concentrations of the drug product available: high dose (OD₆₀₀ 4.0 ± 0.8 equivalent to 8 × 10⁹ cells/mL), middle dose (OD₆₀₀ 2.0 ± 0.4 equivalent to 4 × 10⁹ cells/mL) and low dose (OD₆₀₀ 1.0 ± 0.2 equivalent to 2 × 10⁹ cells/mL).

The middle dose has been selected for this study to minimize the exposure while ensuring administration of a dose considered likely to show improvement in symptoms of atopic dermatitis.

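### Section 6.1.1 gives two dosing rules that cannot both be followed: one pump per 200 cm² of affected skin, and the pump counts in Table 6.2

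*Protocol*

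**What the plan says.** All of this is in Protocol section 6.1.1 unless noted.

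- **The table.** Table 6.2 is headed "Approximate Number of Pumps per application" and runs by age group and by 10, 20, 30 and 50% affected body surface. Families are to use it "to guide the suggested number of pumps to be applied on each application".
- **The palm rule.** The very next sentence says subjects will apply one 0.14 mL pump for every 200 cm² of affected area, described as about one adult palm, twice a day for 28 days. The following paragraph says it twice more: "One pump should cover the surface area of skin the approximate size of one adult sized palm", and "One pump will be applied directly to the skin for each atopic dermatitis area that is the size of a palm" of one adult hand.
- **Who sets the number.** After examining the child, "study staff will instruct the patient on the number of pumps to be applied per application for the duration of the treatment".
- **Limits.** Dispensing is tied to usage, "where the total number of pumps per application should not exceed 16". Section 6.7 repeats the 16-pump figure. On supply: "It is suggested that subjects will use up to the number of bottles indicated in" Table 6.1, with at most six 30 mL bottles.
- **Eligibility.** Sections 4.1 and 5.1 admit 10% to 60% affected body surface; both tables stop at 50%.
- **Dose rationale.** Section 4.3: "The middle dose has been selected for this study to minimize the exposure", where the middle strength is 4 × 10⁹ and the high strength 8 × 10⁹ cells/mL.

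**The concern.** Two adjacent sentences tell the same family how much to apply, and they give different amounts. Staff assign each child a number of pumps, so every child will have a defined dose. Which dose depends on the sentence the site works from, and about six sites are expected.

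In a paediatric safety study the amount applied is part of what the results describe. A twofold difference in volume at the same strength doubles the cells applied, which matches the step from the middle to the high concentration. Section 4.3 chose the middle concentration to limit exposure. Section 6.5 forbids changing the prescribed dosage and wants departures recorded, and section 9.6 asks for the quantity of any excess dose. Both need a single reference amount.

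**Working it through.** **Inputs from section 6.1.1.** One pump = 0.14 mL; palm rule = 200 cm² per pump; 2 × 28 = 56 applications; bottle = 30 mL; caps of 16 pumps and 6 bottles. One pump per application uses 0.14 × 56 = 7.84 mL over the study.

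**Step 1. Does Table 6.2 reproduce Table 6.1?** Bottles = pumps × 7.84 / 30, rounded up, at 10/20/30/50%.

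| Age | Table 6.2 pumps | Bottles computed | Table 6.1 |
|---|---|---|---|
| 2-5 y | 2, 3, 4, 7 | 1, 1, 2, 2 | 1, 1, 2, 2 |
| 6-11 y | 2, 4, 6, 10 | 1, 2, 2, 3 | 1, 2, 2, 3 |
| 12-17 y | 3, 7, 10, 16 | 1, 2, 3, 5 | 2, 3, 4, 5 |

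Nine of 12 cells match exactly; the other three carry one spare bottle. The two tables fit each other, and the largest entry in Table 6.2 equals the 16-pump cap.

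**Step 2. At what body size do the two rules agree?** Total body surface = pumps × 200 cm² / fraction affected. No outside figure is needed.

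- 2-5 y: 0.40, 0.30, 0.27, 0.28 m²
- 6-11 y: 0.40 m² in all four rows
- 12-17 y: 0.60, 0.70, 0.67, 0.64 m²

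Allowing half a pump for rounding raises the largest values only to 0.50, 0.50 and 0.75 m².

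**Step 3. How large is the gap?** Total body surface by age is not in the protocol. Assumed: 0.55-0.80 m² (2-5 y), 0.80-1.25 m² (6-11 y), 1.25-1.90 m² (12-17 y). Palm-rule pumps = min(16, body surface × fraction / 200 cm²). For example, at 6-11 y and 20%, 8,000 × 0.20 / 200 = 8 and 12,500 × 0.20 / 200 = 12.5, against 4 in the table.

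| Age | Affected | Palm rule, capped | Table 6.2 | Ratio |
|---|---|---|---|---|
| 2-5 y | 10% | 2.75-4 | 2 | 1.38-2.00 |
| | 20% | 5.5-8 | 3 | 1.83-2.67 |
| | 30% | 8.25-12 | 4 | 2.06-3.00 |
| | 50% | 13.75-16 | 7 | 1.96-2.29 |
| 6-11 y | 10% | 4-6.25 | 2 | 2.00-3.13 |
| | 20% | 8-12.5 | 4 | 2.00-3.13 |
| | 30% | 12-16 | 6 | 2.00-2.67 |
| | 50% | 16 | 10 | 1.60 |
| 12-17 y | 10% | 6.25-9.5 | 3 | 2.08-3.17 |
| | 20% | 12.5-16 | 7 | 1.79-2.29 |
| | 30% | 16 | 10 | 1.60 |
| | 50% | 16 | 16 | 1.00 |

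Eleven of 12 cells differ. At mid-range body surfaces (0.675, 1.025, 1.575 m²) the ratio in those 11 is 1.6-2.6, and 2.25 or more in eight. With wider assumptions (0.50-0.85, 0.75-1.40, 1.20-2.00 m²) it is 1.25-3.5. The extra volume over 28 days is (2.75 − 2) × 7.84 = 5.9 mL at the least and (16 − 6) × 7.84 = 78.4 mL at the most.

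**Step 4. Palm rule against the limits.** Sixteen pumps cover 16 × 200 = 3,200 cm². For the smallest adolescent assumed that is 3,200 / 12,500 = 26% of body surface, while 60% is eligible. Sixteen pumps use 16 × 7.84 = 125.4 mL, or 4.2 bottles, so the capped palm rule stays under six bottles. It needs more bottles than Table 6.1 lists at every assumed body size in 9 of 12 cells, for example 4-5 against 2 at 6-11 y and 30%.

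**The case against.** The tables are labelled as suggested and approximate, and the palm rule is the directive text, so one could say the table merely helps and the area rule governs. That wording covers rounding; it does not cover a gap of about twofold. The gap is smallest at 2-5 years and 10%, where 3-4 pumps stand against 2. The one cell that agrees does so only because the cap overrides the palm rule.

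Appendix 6, on body surface and application, is not in the text at hand and may say which instruction governs. It still could not make both sentences of section 6.1.1 true.

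The consequences are limited, and that stands. Both readings share the same pump and bottle ceilings, all analyses are descriptive, and section 6.5.2 has bottles weighed at each visit, so actual use can be recovered. Weighing shows what was used afterwards; it does not make the assigned dose uniform.

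A reader might go further and infer that the palm rule is the mistake and should simply be deleted. The documents do not establish that. The palm rule is stated three times and is the only definition of dose per area. The fit of Table 6.1 and the cap to Table 6.2 is weaker evidence than it looks, since both may have been derived from Table 6.2 and would inherit any slip in it. At 400 cm² per pump the table would imply 0.53-0.80, 0.80 and 1.20-1.40 m², so a single factor of two could lie on either side.

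**Conclusion.** The contradiction holds. The body surfaces at which the two rules agree follow from the protocol's own figures and lie below every range assumed here. The size is less certain because it rests on assumed body surfaces: about 1.4-3.2 times after the cap in 11 of 12 cells, or 1.25-3.5 under the wider ranges.

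Table 6.2 capped at 16 pumps is the likelier intent, but that is an inference and the choice is the sponsor's. What suffers is uniform dosing and the ability to state which dose was studied. Neither the definition of the safety endpoints nor the six-bottle limit is affected. The point deserves correction because the change is cheap and concerns the amount children are given.

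**What to change.** The sponsor should confirm the intended dose and state in section 6.1.1 one rule that governs the number of pumps staff assign.

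- **If Table 6.2 is intended:** say that it governs, capped at 16 pumps, and rescale the 200 cm²/palm sentences to match. At the mid-range body surfaces assumed, area per table pump is 338-506 cm² (2-5 y), 513 cm² (6-11 y) and 450-525 cm² (12-17 y), so about 340-525 cm². The cost is one protocol clarification and a site reminder, with no change to supply, visits, eligibility or caps.
- **If the palm rule is intended:** correct Tables 6.1 and 6.2 and reconsider the 16-pump cap. Raising the cap may also reach the bottle limit, since six bottles allow 180 / 7.84 = 22.96 pumps per application. This is a larger change, to supply as well as text.

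An optional minor addition is a 60% row, since 60% is eligible. If the table governs, scaling the 50% row gives 7 × 60/50 = 8.4 (about 8) pumps, 10 × 60/50 = 12 pumps, and 16 pumps by the cap. These use 62.7, 94.1 and 125.4 mL, or 3, 4 and 5 bottles.

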6.2 Preparation/Handling/Storage

All investigational drug supplies in the study will be stored in a secure, refrigerated (2 to 8°C) safe place, under the responsibility of the Investigator or other authorized individual.

The Investigator, or designee will maintain temperature monitoring of the IP with daily temperature readings. All temperature excursions must be reported to the Sponsor using the Temperature Excursion log. If the IP was exposed to the temperature excursion outside the range of 2 to 8°C, but for the period greater than 24 hours, the IP must be quarantined until the Sponsor's approval on future use.

The Investigator or designee must confirm appropriate temperature conditions have been maintained during transit for all study treatment received and any discrepancies are reported and resolved before use of the study treatment.

The Investigator or designee must provide instruction to the subject, and parent or guardian, on the storage requirements for the study treatment.

Only subjects enrolled in the study may receive study treatment and only authorized study center staff may supply study treatment. All study treatments must be stored in a secure, environmentally controlled, and monitored (manual or automated) area in accordance with the labeled storage conditions with access limited to the Investigator and authorized study center staff.

The Investigator, institution, or the head of the medical institution (where applicable) is responsible for study treatment accountability, reconciliation, and record maintenance (ie, receipt, reconciliation, and final disposition records).

Further guidance and information for the final disposition of unused study treatment will be provided.

6.3 Accountability, Destruction and Return of Study Supplies

In accordance with federal and local regulatory requirements, the Investigator and designated site personnel must document the amount of IP dispensed to study subjects, the amount returned by study subjects, and amount received and returned to the Sponsor, when applicable. Product accountability records must be maintained throughout the course of the trial. Any quality issue noticed with the receipt or use of an IP (deficient IP in condition, appearance, pertaining documentation, labeling, expiry date, etc.) should be promptly reported to the Sponsor, who will initiate a complaint procedure.

All IP must be stored in a secure locked room with access limited to the Investigator and designated site personnel. Study product is to be stored in a refrigerator between 2 to 8°C. Maintenance of a temperature log is required.

Under no circumstances will the Investigator or designees allow IP to be used other than as directed by this Clinical Study Protocol, or dispose of investigational product without Sponsor direction.

The Sponsor will supply sufficient quantities of the IP for the completion of this study.

The study pharmacist or designated study personnel will maintain an Investigational Materials Accountability Record and a Subject IP Accountability Log itemizing all IP received, dispensed to and returned from each subject during the study. All dispensed bottles must be accounted for, and any discrepancies explained. Study site should contact site Clinical Research Associate (CRA) or designee in case of any dispensing errors or if discrepancies are discovered.

Prior to site closure and at appropriate intervals during the study, site CRA will perform IP accountability and reconciliation. At the end of the study, the Investigator or designee will retain all the original documentation regarding IP accountability, return, and copies will be sent to the Sponsor.

All unused and used IP tubes will be returned to the Sponsor or its designee for destruction at the end of the study.

